Finally, another possible side effect of regular e-cigarette use is developing an EVALI; however, the likelihood of developing an EVALI while using the SREC is minimal. According to the CDC's recent investigation, EVALI cases were associated with vaping THC and using products purchased from non-licensed vendors (e.g., off the street, from friends or family). In order to minimize the risk of developing an EVALI, enrolled participants must agree to use only the study provided SREC products and to not modify the device or e-liquid in any way. Study staff will provide participants with information and guidance on EVALI from the CDC and instruct participants how to identify the early signs and symptoms of an EVALI. Symptoms reported from the recent EVALI outbreak include: respiratory symptoms, including cough, shortness of breath, or chest pain; gastrointestinal symptoms, including nausea, vomiting, stomach pain, or diarrhea; and nonspecific constitutional symptoms, like fever, chills, or weight loss. Additionally, study staff will assess presence and severity of symptoms associated with EVALI along with any e-cigarette products used (SREC or non-SREC) at each study visit and include this information with any potential AE or SAE reporting.

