## **11.0 Data and Safety Monitoring**

This trial will be monitored by [name]. (PI), [name]. (Co-I), [name] (Data Manager), and an independent Data Safety Monitoring Board (DSMB) that will be chaired by a medical safety monitor: [name], MPH, FAAP, Professor of Pediatrics, College of Medicine, UIC. The DSMB will meet at the start of the trial to review the study protocol, safety and ethical issues, and to approve plans for data integrity. [name], [name], and [name] will meet weekly during the data collection phase to review and monitor the following items: participant accrual, participant complaints, participant drop-out, reasons for drop-out, adverse events, and any other problems related to study participation. Data accuracy and completeness will also be monitored weekly. During active recruitment, the DSMB will join these data review meetings quarterly to monitor participant safety.

The data report will be updated on a weekly basis and will include: participant accrual, participant complaints, participant drop-out, reasons for drop-out, adverse events, and any other problems related to study participation. The report will also include preliminary data on cigarette and SREC usage on a participant basis.

An AE is defined as any untoward medical or psychological event experienced by a patient during or as a result of his/her participation in the study that represents a new symptom or an exacerbation of an existing condition whether or not considered study-related based on appropriate medical judgment. SAEs are any adverse experience that results in any of the following outcomes: death, life-threatening event/illness, inpatient hospitalization or prolongation of existing hospitalization, persistent or significant disability/incapacity, pregnancy resulting in a congenital anomaly/birth defect, or any event requiring medical or surgical intervention to prevent permanent impairment or damage. In this study, this is defined as physician confirmed diagnosis of any of the following: angina pectoris, heart attack, stroke, transient ischemic attack, heart failure, coronary angioplasty or bypass surgery, peripheral vascular disease, and cancer (except for non-melanoma skin cancer). Non-SAEs are all adverse events that do not meet the above criteria for "serious."

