AEs will be systematically identified by querying participants at each of the in-person data collection time points after the start of treatment (week 2) through end of treatment (i.e., at weeks 3, 4, 6, 8, 11, and 14) using a standardized AE Patient Query Form to be adapted from [name] prior research studies using NRT while reducing cigarettes. AEs discovered outside of those planned evaluations, such as through other administrative interactions between research staff and participants (e.g., appointment reminder or rescheduling calls), will also be documented using the standardized AE form and followed up with to assure participant safety. Research staff will complete the AE forms directly into a centralized REDCap database in these circumstances. [name] will receive an automatic notification from REDCap upon submission of every AE report in order to trigger a review. The study safety monitor ([name]) will review, adjudicate, and document decisions or request that additional details be gathered from the participant, all

within the secure UIC REDCap web portal. Using this system, real-time AE reports can be generated at any time for the DSMB, UIC IRB, and/or NIDA, for both regularly scheduled reviews as well as in the event of any SAEs requiring expedited reviews.

**Expedited reporting.** All unexpected SAEs will be reported to the DSMB within 5 business days of discovery, regardless of any judgment of their relatedness to the study treatment. This reporting timeframe is consistent with the UIC IRB's requirements as described below. All relevant information will be reported to the DSMB for each unexpected AE including information about the event and its outcome, dosing history of a suspect medication/treatment, concomitant medications, the participant's medical history and current conditions, and all relevant laboratory data. An initial notification with all related study forms shall be made to the DSMB within 72 hours of the detection of an unexpected SAE. Any additional information about the case that may be obtained after the initial notification shall be communicated to the DSMB in a timely manner. The DSMB may require a conference call to review all the relevant information and the study safety monitor's determination of whether there was any possible relevance to the study and discuss and approve a Corrective and Preventive Action Plan, if warranted.

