### **13.3 Unanticipated Problems (UPs)**

All staff who work directly with study participants are trained to notify [name] of any UPs resulting from study participation immediately on discovery. UPs may also be reported through participant Adverse Event reporting at each study visit. [name] will receive an automatic notification from REDCap upon submission of every AE report in order to trigger a review. In addition, the Data Safety Monitoring Board will meet and review any UPs. [name], [name], and [name] will meet weekly during the data collection phase to review and monitor the following items: participant accrual, participant complaints, participant drop-out, reasons for drop-out, adverse events, and any unanticipated problems related to study participation. During active recruitment, the DSMB will join these data review meetings quarterly.

All serious unanticipated problems will be reported to the IRB within 24 hours. Serious events are described as untoward medical occurrence that results in death, is life-threatening, requires inpatient hospitalization or prolongation of hospitalization, creates persistent or significant disability/incapacity, or a congenital anomaly/birth defect. The probability of such occurrences as part of this study is extremely low. Nevertheless, an appropriate Data and Safety Monitoring Plan is in place. If such an event occurs, the PI will immediately notify the entire Data and Safety Monitoring Board and the IRB within 24 hours. The Office of Protection of Research Subjects (OPRS) at the University of Illinois at Chicago has procedures in place to review reports, and the PI is notified if further review, changes to the research protocol or consent form, or other action is required. [name] will notify NIDA should the UIC IRB review require further action after any serious unanticipated problem is reported.

UIC OPRS also defines unanticipated problems as a breach of confidentiality or subject complaints. OPRS requires that all incidents be reported within ten working days of discovery. For all unanticipated problems, sufficient information shall be obtained from the PI in order to gauge severity and to complete the mandatory OPRS report form. UIC OPRS has procedures in place to review the report form, and the PI is notified if further review, changes to research protocol or consent form, or other action is required.

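### The SAE definition can be read as limited to cardiovascular diagnoses and cancer, leaving out EVALI and nicotine toxicity, and the DSMB and IRB reporting times conflict

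*Combined protocol and SAP*

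**What the plan says.** **Definition.** Section 11.0 (Data and Safety Monitoring) starts from outcomes: "SAEs are any adverse experience that results in any of the following outcomes: death, life-threatening event/illness, inpatient hospitalization or prolongation of existing hospitalization", then disability, congenital anomaly, and events needing intervention to prevent permanent damage. The next sentence reads: "In this study, this is defined as physician confirmed diagnosis of any of the following: angina pectoris, heart attack, stroke". The list goes on to transient ischemic attack and then "heart failure, coronary angioplasty or bypass surgery, peripheral vascular disease, and cancer (except for non-melanoma skin cancer"). The residual class follows: "Non-SAEs are all adverse events that do not meet the above criteria for" serious. Section 13.3 (Unanticipated Problems) defines serious events by outcome only and has no list of diagnoses.

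**Named product risks.** Section 6.2 (SREC Intervention) says that "another possible side effect of regular e-cigarette use is developing an EVALI", while calling the likelihood minimal. It also describes nicotine toxicity. Symptoms of both are to be assessed at each study visit.

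**Deadlines.** The Expedited reporting paragraph appears twice in section 11.0. Both copies say: "All unexpected SAEs will be reported to the DSMB within 5 business days of discovery". Both also say: "An initial notification with all related study forms shall be made to the DSMB within 72 hours of the detection of an unexpected SAE". Section 13.3 says that, for a serious event, "the PI will immediately notify the entire Data and Safety Monitoring Board and the IRB within 24 hours". Section 6.2 and the paragraph on management of SAEs in section 11.0 send SAEs to the medical monitor and the IRB immediately. The paragraph on IRB requirements in section 11.0 allows 5 business days for an unanticipated AE and 15 business days for a non-SAE.

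**The concern.** The wording of the sentence that introduces the list is limiting: it defines, and does not say that the diagnoses are examples or additions. None of the eight entries is respiratory or toxicological, so the two risks that the protocol attaches to the product are absent from the study-specific definition. If staff apply the sentence as written, a hospital admission for EVALI is a non-SAE, while an angina diagnosis made in an outpatient clinic is an SAE.

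Classification decides the route. The expedited path to the DSMB is open only to unexpected SAEs, and the trial has no formal stopping rules for safety (section 11.0, Trial Stopping Rules). At stake is whether a serious lung or nicotine event reaches the board promptly or waits for a slower channel. The conflicting deadlines are a second, separate problem: two staff members could follow different paragraphs for one event and both be compliant.

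**Working it through.** No sample size, power or alpha figure bears on this point. The check sets the passages side by side and converts business days to calendar days.

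**1. What the list contains.** Angina, heart attack, stroke, transient ischemic attack, heart failure, coronary angioplasty or bypass, peripheral vascular disease: seven entries. Cancer, apart from non-melanoma skin cancer: one. Total 7 + 1 = 8, with none respiratory or toxicological.

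**2. How a hospitalised EVALI case is classified.**

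| Reading | Class of event |
|---|---|
| 11.0, outcome criteria govern | SAE (hospitalisation) |
| 11.0, list replaces the outcomes | Non-SAE |
| 13.3, outcomes only | Serious |

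A hospitalised nicotine-toxicity case gives the same three answers. The outcome sets in 11.0 and 13.3 also differ slightly: 11.0 includes intervention to prevent permanent damage and 13.3 does not.

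**3. Calendar time.** Count the day of discovery as day zero and ignore holidays.
- 5 business days: from a weekday, 5 + 2 weekend days = 7 calendar days; from a Saturday, 6; from a Sunday, 5. The range is 5 to 7 days, or 5 × 24 = 120 to 7 × 24 = 168 hours.
- 15 business days: from a weekday, 15 + 6 = 21 calendar days; from a Saturday, 20; from a Sunday, 19. The range is 19 to 21 days.

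**4. Deadlines for an event that is both an unexpected SAE and a serious unanticipated problem.**

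| Recipient | Time | Where stated |
|---|---|---|
| DSMB | immediately | 13.3 |
| DSMB | 72 hours | 11.0, Expedited reporting (both copies) |
| DSMB | 5 business days (120 to 168 hours) | 11.0, Expedited reporting (both copies) |
| IRB | immediately | 6.2; 11.0, management of SAEs |
| IRB | 24 hours | 13.3 |
| IRB | 5 business days, for an unanticipated AE | 11.0, IRB requirements |

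Ratio of the longest limit to the 24-hour limit: 120/24 = 5 to 168/24 = 7. Reports to the FDA portal are to follow the same timeline as those to the IRB and NIDA (section 11.0), so they inherit the conflict.

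**5. Effect of the narrow reading on timing.** Classed as an unexpected SAE, the event reaches the DSMB within 5 business days at the latest. Classed as a non-SAE, it leaves that route and falls under the 15-business-day rule, 19 to 21 calendar days, in a paragraph about the IRB rather than the DSMB. The exception is an event judged unanticipated, which would go by section 13.3 if serious. That exception is uncertain for EVALI: because section 6.2 lists it as a possible side effect, someone could call it anticipated.

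**The case against.** The sentence with the list never says that it is exclusive, and *this* has no clear antecedent. It directly follows the criterion on intervention to prevent permanent damage and may explain only that. As a full replacement, it would turn a death from any unlisted cause into a non-SAE and empty the sentence before it. The non-SAE sentence refers to criteria in the plural, which fits the outcomes. Section 6.2 attaches EVALI symptom data to possible AE or SAE reports, so the authors evidently thought that such an event could be an SAE. All of this stands as evidence of intent. It does not remove the defining words, and staff will work from those.

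On deadlines, the rules have different scopes: unexpected SAEs, unanticipated AEs, and serious unanticipated problems. The 72-hour step is an initial notification with further information to follow, which suggests two stages, and meeting the shortest limit meets them all. This stands in part. The classes overlap, the 72-hour notice already requires all study forms, no text says that there are two stages, and section 13.3 is stricter than both.

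A reader might infer four stronger points that the documents do not support:
- *That SAE reports are the DSMB's only trigger.* The board joins data reviews quarterly, meets as needed on problematic adverse events, and may recommend termination at its discretion (sections 6.2 and 11.0). Every AE report triggers an automatic notification and review by the safety monitor.
- *That SAE tables would be wrong.* The analysis sections (9.0 and 12.0) plan none.
- *That the deadlines cause under-reporting.* They can make reports late or inconsistent. Only the definition affects what is classed as an SAE.
- *That section 11.0 misstates the IRB requirement.* Its 5-business-day statement matches the IRB paragraph that follows it. The 24 hours in section 13.3 is a commitment by the study, not a stated IRB rule.

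**Conclusion.** The point holds as a defect of wording with a practical consequence. On the literal reading of section 11.0, hospitalised EVALI and nicotine-toxicity cases are non-SAEs, which contradicts section 13.3. The harm is misclassification and late escalation, not loss of the event: a limit of 19 to 21 calendar days outside the DSMB's expedited route, against at most 5 to 7 days to the DSMB inside it. This rests on staff taking the list as the operative definition, and on the event not being rescued by section 13.3 as unanticipated. If the list was meant as illustration, or as a gloss on the last criterion alone, the outcome criteria already capture these cases and only clarity is missing.

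The deadline conflict does not depend on that reading. For an event in both classes there are three DSMB times and three IRB times, with a 5- to 7-fold spread from 24 hours to the longest. If 72 hours and 5 business days are two stages, the conflict within section 11.0 disappears, but the conflict with section 13.3 remains. Neither problem touches an endpoint, the randomisation or an efficacy analysis. Both should still be corrected, because the entry criterion for expedited review is unclear for the risks that the protocol itself names.

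**What to change.** 1. State in sections 11.0 and 13.3 that one identical set of outcome-based criteria governs, and settle whether intervention to prevent permanent damage belongs to it.
2. Recast the diagnosis list as additional: diagnoses always handled as serious, whatever the outcome. Include EVALI in it.
3. Replace the scattered deadlines in sections 6.2, 11.0 (both copies of the Expedited reporting paragraph, IRB requirements, management of SAEs) and 13.3 with one timetable by event type and recipient: medical monitor, DSMB, IRB, NIDA and FDA portal. If 72 hours and 5 business days are two stages, say so and state what each report contains.
4. In the same timetable, say whether an event that the protocol lists as a possible side effect counts as unexpected or unanticipated. Otherwise an EVALI case classed as an SAE could still miss the DSMB's expedited route.

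The cost is an amendment to the protocol wording, the AE form and the staff training material, and possibly a few more expedited reports. Sample size, analysis and treatment are unchanged.

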At each study visit following week 2, adverse events (AE) and unexpected problems (UPs) with the SREC are collected using a standardized AE Patient Query Form adapted from [name] prior research studies using NRT while reducing cigarettes. This form is stored in a REDCap database. AEs discovered outside of study visits, such as through a phone call or other administrative contact (e.g., appointment reminder or rescheduling calls), will also be documented using the standardized AE form and followed up with to assure participant safety. Clinical staff interviewers are the first line of staff to monitor and assess AEs and UPs. Staff are instructed to notify [name] of these events so that a plan to can be put into place and appropriately monitored. However, [name] will also receive an automatic notification from REDCap upon submission of every AE report in order to trigger a review. The study safety monitor ([name]) will review, adjudicate, and document decisions or request that additional details be gathered from the participant, all within the secure UIC REDCap web portal. Using this system, real-time AE reports can be generated at any time for the DSMB, UIC IRB, and/or NIDA, for both regularly scheduled reviews as well as in the event of any SAEs requiring expedited reviews. SAEs will be immediately reported to the medical monitor, [name] and to the IRB. [name] will address these with the participant to ensure that the participant is linked with appropriate follow-up medical care.

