Adverse Events (e.g., throat irritation, nausea)			x	X	x	x	x	x	x	x	x	x	x	x		

A. A **Comprehensive questionnaire** (baseline and 14-Week End of Treatment visits) will be completed in-person to assess key constructs [e.g., sociodemographics, tobacco and nicotine use (history, dependence, attitudes, motivations, intentions, perceived harm), tobacco environment, cessation history and intentions, and other substance use]. Each questionnaire will take approximately 30 - 40 minutes to complete. Shorter **brief surveys** (5-7 minutes to complete) will be completed at weeks 2, 3, 4, 6, 8, and 11. These measures serve as important descriptors of our sample, serve as covariates or moderators in our analyses, and serve as predictors of success in reducing cigarettes and switching to SREC over time.

B. A **daily use survey** completed online via REDCap from an emailed or texted survey link starting at the week 2 visit through the week 14 visit (over the 12 treatment weeks) to assess the use of cigarettes, SREC, and any other e-cigarette/nicotine vaporizer. Each of these surveys will take about 1 minute to complete. This brief survey will serve as an indicator of change in patterns of use as well as a way for the Clinical Interviewer Staff to track progress with cigarette reduction and to monitor nicotine exposure during the treatment phase. Daily surveys ask about the number of cigarettes smoked and the number of SREC or other e-cigarette episodes on the previous day (an episode is defined as 15 puffs or a period lasting about 10 mins). We also ask if the participant finished a pod on the previous day.

C. **Two, week-long waves of EMA data collection** using a **study provided smartphone**, the first wave will take place immediately following completion of the baseline questionnaire (week 1 visit through week 2 visit), and the second wave will take place starting at the week 3 visit through the week 4 visit. The first week of EMA provides the baseline comparison with combustible cigarettes to the second EMA wave when participants will have one week of experience with using the SREC and some practice cutting down on their cigarette smoking. Each EMA wave will cover 7 consecutive days, ensuring both weekday and weekend sampling.

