We will discuss potential risks with participants at study enrollment and consent. We will discuss with participants that all tobacco use may present some harm, and that no tobacco use is healthy. We will also provide education to participants on the symptoms of nicotine toxicity (nausea and vomiting) so that they are aware and can reduce their exposure if they experience these symptoms. We also will provide participants with education on the recent outbreak of EVALI cases and how to identify if they may be experiencing the early signs and symptoms of an EVALI. At the enrollment visit (during the consent process) and at the end-of-treatment visit, we will tell participants that the long-term safety and health effects of using e-cigarettes is unknown. We will also discuss in-person and include on the information sheet that the SREC device may contain nicotine which can be hazardous to children and pets if ingested, in addition to informing the risk of nicotine use for pregnant and/or nursing women. We plan to discuss the safe and secure storage of the device and pods in their homes. Additionally, we will clearly label the SREC packaging so that participants are aware the SREC is used "for investigational purposes only."

Clinical study staff are the first line of staff to monitor and assess AEs and UPs. These will be assessed at each study visit after week 2. They will be recorded in REDCap responses to short surveys and in written responses to interview questions. Staff will notify [name] about these events during weekly supervision, but [name] will also receive emails as Adverse Event Reports are submitted to the REDCap database. Plans will be developed to manage and monitor AEs and UPs. SAEs will be immediately reported to the medical monitor, [name]. [name] will address these with the participant to ensure that the participant is linked with appropriate follow-up medical care. In our REDCap database, we will have a programmed report for AEs and UPs that can be run as needed for review to ensure that our understanding of adverse events and problems is always up to date.

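### An adverse event must be a new or worsened symptom, but the AE form is first used after SREC starts and no baseline symptom record is tied to AE classification

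*Combined protocol and SAP*

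**What the plan says.** Section 11.0 defines an AE as an untoward medical or psychological event that "represents a new symptom or an exacerbation of an existing condition whether or not considered study-related based on appropriate medical judgment".

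The timing of systematic collection is given in four places, and they agree that it starts after week 2:

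- Section 11.0: "AEs will be systematically identified by querying participants at each of the in-person data collection time points after the start of treatment (week 2", continuing "through end of treatment (i.e., at weeks 3, 4, 6, 8, 11, and 14) using a standardized AE Patient Query Form".
- Section 6.2: "At each study visit following week 2, adverse events (AE) and unexpected problems (UPs) with the SREC are collected".
- Section 11.0, on management of SAEs and other study risks: "These will be assessed at each study visit after week 2".
- Section 6.3, Table 2: the row "Adverse Events (e.g., throat irritation, nausea" (and so on) is blank at weeks 1 and 2 and marked from week 3.

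Table 1 (section 6.0) and section 6.2 place the first SREC supply at the week 2 visit.

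Two other statements in section 6.2 point to a wider schedule. One says nicotine-toxicity symptoms are assessed at every study visit. The other says the presence and severity of EVALI symptoms, which include "respiratory symptoms, including cough, shortness of breath, or chest pain", are assessed at each study visit. Neither assessment has its own row in Table 2.

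**The concern.** The words new and exacerbation both call for a comparison with the participant's state before treatment. The effects that section 6.2 expects from SREC, such as cough, throat irritation, nausea and headache, are common and nonspecific, and a daily smoker may already have some of them. If the first systematic query comes a week after SREC is dispensed, a long-standing symptom can be logged as an SREC event. A true worsening may also be hard to recognise.

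The classification has consequences. Under section 6.2, AE reports feed coaching and can lead the PI, the medical monitor or the DSMB to stop dispensing pods. Under section 11.0 they go into reports to the DSMB, the IRB and NIDA, and SREC adverse experiences are to be reported to FDA. Both arms receive SREC (section 6.0), so there is no unexposed group. Each participant's own pre-SREC state is the main reference for tolerability.

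**Working it through.** The documents state no AE rate, safety power or AE sample size, so there is no figure to reproduce. The check sets the schedule against the definition.

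**Step 1: timing.** First SREC supply: week 2. Scheduled AE form uses: weeks 3, 4, 6, 8, 11 and 14. Uses before SREC = 0; uses after = 6.

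**Step 2: what else is recorded before SREC.** Table 2 gives the respiratory questionnaire (SGRQ) at weeks 1, 14 and 18, medical history at week 1, and withdrawal scales at weeks 1 and 2 and at later visits. The first EMA wave runs from the week 1 visit to the week 2 visit (section 6.3). Set against the more common effects listed in section 6.2:

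| Listed effect | Pre-SREC record named in the documents | Limit |
|---|---|---|
| Cough | SGRQ, week 1; EVALI check if the each-visit wording is literal | SGRQ is not repeated until week 14; its items are not shown |
| Nausea | EMA item on feeling sick; toxicity and EVALI checks if the wording is literal | EMA item belongs to product-use recordings |
| Throat irritation | EMA item | Follow-up questions depend on the product; use for cigarettes is not stated explicitly |
| Headache, dizziness, mouth irritation | None named | Also absent from section 6.2's toxicity and EVALI symptom lists |

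Shortness of breath, listed as less frequent, is in the same position as cough. The last row matters most: even if the toxicity and EVALI checks do take place at weeks 1 and 2, those three effects are still not covered by any named item.

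**Step 3: is any of this tied to AE classification?** Section 11.0 lets the safety monitor adjudicate each report and ask for more detail. Expedited reports to the DSMB carry medical history and current conditions. Nothing says that the SGRQ, the withdrawal scales or the EMA data are consulted, or how a report is judged new or worsened.

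**Step 4: effect on the arm comparison.** Participants are randomised 1:1 within sex, 60 per arm, and both arms have the same AE schedule. Pre-existing symptoms balance in expectation, so they add noise to a between-arm AE comparison but no bias.

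**Step 5: scale, as an assumption only.** The number of people carrying at least one listed symptom into the trial is N × p. With N = 120 and an assumed p of 0.20 to 0.40, that is 120 × 0.20 = 24 to 120 × 0.40 = 48. For that assumed range, this is a ceiling on how many could report a pre-existing symptom as an AE. It supposes that every such symptom is reported and that none is filtered by the form, the interviewer or the safety monitor.

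**The case against.** The definition does not demand that the same instrument be used before treatment. New or worsened status can be settled from reported onset, medical history and adjudication. The AE form is still to be adapted and is not reproduced, so it may already ask about onset. Current respiratory conditions such as asthma and COPD are excluded (section 4.2). Section 9.0 plans no AE analysis, so no hypothesis test depends on this.

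Much of that stands, and it rules out three stronger readings that a reader might infer:

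- *That pre-existing symptoms cannot be told apart from new ones, or that the definition cannot be applied.* Several symptoms have some pre-SREC record, and the safety monitor can query any case.
- *That an early lung-injury signal would have nothing to be compared with.* The SGRQ is given at week 1, and section 6.2, read literally, puts EVALI symptom checks at the first two visits. What the documents show is an unresolved scheduling conflict, not an absence of data.
- *That some number of false AEs will occur.* The documents give no background prevalence, and the illustration above is a ceiling under an assumption.

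What does not answer the point is reliance on later queries. Detail gathered after exposure is recall, not a prospective record, and no rule brings the existing baseline instruments into the judgment.

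**Conclusion.** The point holds in a limited form. The AE form has no pre-SREC administration (0 of 6 scheduled uses), no baseline measure is linked to AE classification, and three listed effects (headache, dizziness, mouth irritation) have no named pre-SREC item. For several listed symptoms, new versus pre-existing status depends on recall and individual judgment. This weakens attribution within participants and leaves the randomised comparison unbiased. Its numerical size cannot be derived from the documents.

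The conclusion assumes that the AE form is used only on the stated schedule, and that instruments whose items are not shown contain no further relevant symptoms. If the form asks about onset and prior severity, the gap narrows to the quality of recall. The matter is a cheap improvement to safety data and does not threaten the trial's primary result. It has to be made before a participant starts SREC, because the record cannot be recovered afterwards.

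**What to change.** 1. Give the existing AE Patient Query Form, with the EVALI and nicotine-toxicity items, once at the week 2 visit before SREC is dispensed, and add the week 2 mark to the Adverse Events row of Table 2.
2. State in section 11.0 that this record goes to the safety monitor and the DSMB as the reference for judging whether a later report is new or worsened. Continue to record every later report. The baseline record should not exclude reports automatically: a symptom present at week 2 may resolve and then recur on SREC, and a hard rule could suppress it.
3. Reconcile section 6.2's statements that toxicity and EVALI symptoms are assessed at every or each visit with the after-week-2 schedule in sections 6.2 and 11.0 and in Table 2.

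The cost is a few minutes at a visit already planned at 60 minutes, using a form that is already planned. A baseline form has a limit: both arms take up SREC while cutting down cigarettes, so it shows what was there before but cannot separate the effects of SREC from those of smoking less.
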